4.8 Study withdrawal and replacement

4.8.1 Subject withdrawal

Subjects have the right to withdraw from the study at any time for any reason. Should a subject decide to withdraw from the study, all efforts should be made to complete and report the observations as thoroughly as possible.

4.8.2 Replacement policySubjects withdrawing will be replaced at the discretion of the investigator.

5 INVESTIGATIONAL MEDICINAL PRODUCT

Not applicable.

5.1.1 Blinding

Not applicable.

6 CLINICAL ENDPOINTS

6.1 Clinical endpoints

- Concomitant medication
- Clinical laboratory tests
 - Haematology
 - Urinalysis
- Vital signs
 - Pulse Rate (bpm)
 - Systolic blood pressure (mmHg)
 - Diastolic blood pressure (mmHg)

6.2 CNS outcome variables

NeuroCart tests:

- Adaptive tracking:
 - average performance (%);
- Visual Verbal Learning Test (VVLT) memory testing
 - o immediate recall 1 (number correct),
 - o immediate recall 2 (number correct),
 - o immediate recall 3 (number correct),
 - o delayed recall (number correct),
 - o delayed recognition (number correct), and
 - o delayed recognition (average reaction time correct) (msec).
- Milner Maze test:
 - o Immediate
 - Total errors
 - Total moves
 - Time (msec)
 - Reversed
 - Total errors
 - Total moves
 - Time (msec)
 - Delayed
 - Total errors
 - Total moves
 - Time (msec);
- Face Encoding and Recognition Task:
 - o Average reaction time for number correct recognition task;
 - Number correct recognition task;
- N-Back task:
 - (nr correct-nr incorrect)/total for zero-back

- o (nr correct-nr incorrect)/total for one-back
- o (nr correct-nr incorrect)/total for two-back
- o average reaction time for zero back (msec)
- o average reaction time for one back (msec)
- average reaction time for two back (msec);
- Sustained Attention to Response Task:
 - Total errors:
 - Total number of omission errors;
 - Total number of commission errors:
 - Mean reaction time correct responses;
 - Reaction time variability;
 - Post error slowing score.
- Finger tapping:
 - Mean tapping rate;
 - Standard deviations.

Neurophysiological NeuroCart assessments:

The following EEG endpoints will be determined at each time point and summarized:

Primary:

- Alpha-power Fz-Cz (uV)
- Alpha-power Pz-O1 (uV)
- Alpha-power Pz-O2 (uV)
- Beta-power Fz-Cz (uV)
- Beta-power Pz-O1 (uV)
- Beta-power Pz-O2 (uV)
- Gamma-power Fz-Cz (uV)
- Gamma-power Pz-O1 (uV)
- Gamma-power Pz-O2 (uV)
- Delta-power Fz-Cz (uV)
- Delta-power Pz-O1 (uV)
- Delta-power Pz-O2 (uV)
- Theta-power Fz-Cz (uV)
- Theta-power Pz-O1 (uV)
- Theta-power Pz-O2 (uV)

When primary EEG endpoints show results that warrant further analysis in the opinion of the investigator, further analysis will be performed and will be described in the SAP.

- Saccadic eye movements:
 - o saccadic reaction time (second),
 - o saccadic peak velocity (degrees/second), and
 - saccadic inaccuracy (%);
- Smooth pursuit eye movements:

o percentage of time the eyes of the subjects are in smooth pursuit of the target (%).

Neuropsychological tests

- GDS-15 (only at screening):
 - Total score
- MMSE (only at screening):
 - Total score
- CDR:
 - Sum of boxes
- IADL:
 - Total score

Handgrip strength

o Handgrip strength dominant hand

6.3 Biochemical endpoints

CSF biomarkers

- Aβ concentration (1-40, 1-42 and 1-42/1-40 ratio);
- T-Tau and p-Tau concentrations;
- NfL concentration.

Plasma markers

- Aβ concentration (1-40, 1-42);
- T-Tau and p-Tau concentrations;
- NfL concentration.

Exploratory biomarkers including but not limited to:

- Synaptic loss; Neurogranin [24],
- Glial inflammation; YKL-40 [25],
- Levels of p-Tau181 in extracts of neutrally-derives blood exosomes [26],
- MicroRNAs [MiR-155, MiR-107 and MiR-29 [27]]).

Genetic assessments

• APOE ε genotype.

7 STUDY ASSESSMENTS

See Table 1 for the time points of the assessments.

7.1 Clinical assessments

A short physical examination is performed before study participation to check if a subject is eligible e.g. has no general health problems, no comorbidities which might influence study participation and/or the study endpoints.

7.1.1 Vital signs

Evaluations of systolic and diastolic blood pressure, pulse rate, and temperature will be performed at screening. Pulse and blood pressure will be taken after 5 minutes in the supine position, thereafter the blood pressure will be measured in a standing position. There will be a gradual transition to the erect position. Automated oscillometric blood pressures will be measured using a Dash 3000, Dash 4000, Dynamap 400 or Dynamap ProCare 400. Additionally, the pulse rate data is provided by the pulse oximeter attached to the monitor.

7.1.2 Weight and height

Weight (kg) will be recorded at screening. Height (cm) will be recorded and body mass index (BMI) calculated at screening. Also the waist/hip ratio will be measured at screening as BMI and the waist/hip ratio is associated with worse cognitive functioning at later age [29].

7.1.3 Physical examination

Physical examination (i.e., inspection, percussion, palpation and auscultation) is performed during the screening. Clinically relevant findings that are present prior to study participation must be recorded with the subject's Medical History. Clinically relevant findings found after the start of study participation and meeting the definition of an adverse event (AE, new AE or worsening of previously existing condition) must be recorded.

7.1.4 Laboratory assessments

Laboratory parameters

Blood and other biological samples will be collected during screening for the following clinical laboratory tests:

Lab	Tests	Collection & Analysis
Haematology	Haemoglobin [including Mean Corpuscular volume (MCV), Mean corpuscular haemoglobin (MCH), Mean corpuscular haemoglobin concentration (MCHC)], haematocrit, red cell count (RBC), total white cell count (WBC), leukocyte differential count and Platelet count. Differential blood count, including: basophils, eosinophils, neutrophils, lymphocytes, and monocytes.	4 mL of venous blood in a BD Vacutainer® K2EDTA tube. Samples will be analysed by the Central Clinical Hematology Laboratory (CKHL) of Leiden University Medical Center.
Serology	HIV1 and HIV2 antibodies, Hepatitis B antigen and Hepatitis C antibodies	5 mL of venous blood in a BD Vacutainer® SST Gel and Clot Activator tube. Samples will be analysed by the Central Clinical Microbiology Laboratory (CKML) of the Leiden University Medical Center.
Urinalysis	Leucocytes, blood, nitrite, protein, urobilinogen, bilirubin, pH, specific gravity, ketones, glucose. If there is a clinically	A midstream, clean-catch urine specimen will be analysed by dipstick (Multistix® 10 SG,

	significant positive result, urine will be sent to the CKCL for microscopy and/or culture.	Siemens Healthcare Diagnostics, Frimley, UK).
Alcohol	Alcohol Breath Test	The hand-held Alco-Sensor IV meter (Honac, Apeldoorn, the Netherlands) will be used to measure the breath ethanol concentrations.
Urine drug screen	Cocaine, amphetamines, opiates (morphine), benzodiazepines and cannabinoids.	A urine specimen will be analysed at CHDR by test kit (InstAlert, Innovacon, San Diego, USA).

DNA collection

Genotypes of the APOE ϵ gene have been shown to be relevant for amyloid metabolism and deposition. The APOE ϵ 4 genotype is associated with the risk to develop AD, but as well with higher amyloid load in the brain in healthy elderly and patients with AD [30]. A blood sample of 4mL will be collected in a K2EDTA tube according to standard operating procedures. Samples will be stored at -80° C. Remaining blood from the samples will be used for future exploratory DNA research after which possible remaining samples will be destroyed.

CSF sampling

A CSF sample for estimation of Aβ concentration (1-40, 1-42 and 1-42/1-40 ratio), Total tau concentration, Phosphorylated tau concentration and Neurofilament Light will be collected at a predetermined time point, see Table 1. A recent study by Janelidze et al., (2016) concluded that calculating the ratio between Aβ40/Aβ42 is significantly better in detecting amyloid deposition in prodromal AD and to differentiate AD patients from healthy elderly than (only) measuring lowered Aβ42 and will therefore also be calculated in the current study [31]. Apart from the standard assessments used for the diagnosis of Alzheimer's disease as Aβ concentrations and Tau, Neurofilament Light will also be determined. Neurofilament light (NfL) chain is a putative marker of subcortical large-caliber axonal degeneration and increased NfL in CSF has been linked to inflammatory diseases, frontotemporal lobe dementia and AD [32]. Recent studies have found that NfL is associated with AD disease progression and that NfL correlates with cognitive performance over time [33]. Also the presence of white matter changes was associated with increased levels of NfL, which probably reflects axonal degeneration [34], this in turn will cause worse cognitive performance.

A CSF sample of 4 mL will be collected in a 10 mL polypropylene tubes and transferred to the lab. Time of sampling is recorded. CSF is centrifuged within one hour, at 2000g for 10 minutes at 4°C. Prior to centrifugation, CSF samples are kept at room temperature. Immediately after centrifugation, samples are divided into 0.5 ml aliquots in clean Sarstedt polypropylene 0.5 mL tubes and stored at –80°C. All aliquots are clearly labeled. Lumbar punctures will be performed by a trained, physician with a 25 G atraumatic lumbar puncture needle (Braun, 25G), who will be supervised by an experienced neurologist. The needle will be placed at the L3-L4 or L4-L5 interspace with the subject in supine or sitting position. If a subject suffers from post-dural headaches, the subject will be treated according to our standard operating procedures.

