Plasma levels of Aβ40, Aβ42 and NfL, APOE ϵ status and NeuroCart tests of the 200 subjects willing to undergo a lumbar puncture will be used to define an algorithm that will be able to improve the efficiency of finding subjects who have an Aβ positive (CSF) profile. The subjects will be divided in a group yielding subjects who are suspected of AD pathology (ADpath+) by the algorithm and subjects who are suspected to be without AD pathology (ADpath+). To confirm the correct classification potential of the algorithm, the outcome will be compared to the CSF Aβ outcome of the subjects. CSF ADpath+ and a CSF ADpath- defined by an Aβ 1-42 CSF level ≤450 pg/mL for ADpath+ subjects and an Aβ 1-42 CSF level ≥451 pg/mL for ADpath- subjects, will be used to differentiate between the two groups (using the Single Molecule Array assay; Simoa assay [19]).

If the ability of the algorithm to discriminate between subjects who are likely to have a biomarker profile indicative of AD pathology and subjects with a normal biomarker profile is confirmed by evidence of pathology in CSF, it could be decided to not perform lumbar punctures in subjects who are very likely to have a *normal* CSF biomarker profile based on the algorithm in future studies. This will allow for a noninvasive method to pre-select healthy subjects likely to have A β pathology in the CSF and therefore to fewer healthy elderly subjects who will have to undergo a lumbar puncture. The results of this study can also be used for subject selection for research that specifically targets a certain biomarker (e.g NfL).

As an exploratory objective, plasma samples will be analyzed for diurnal fluctuation in this current study. Diurnal fluctuation in the concentration of CSF biomarkers has been reported and may represent a pre-analytical confounding factor in the laboratory diagnosis of AD [20]. Plasma biomarkers for AD have however not been extensively studied for possible fluctuating levels during the day. The results will also provide more information about the effect of the clearance systems of the brain which removes proteins (e.g. $A\beta$) from the brain via various overlapping clearance systems [21]. These clearance systems may be the cause of the diurnal fluctuation reported in CSF. This knowledge can be used in future clinical trials to perform certain assessments (e.g. LP and blood samples) at the most useful time points.

Objective(s)

Main objectives:

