2 STUDY OBJECTIVES

Main objectives:

To define an algorithm based on the plasma biomarkers: A β 40, A β 42, t-Tau, p-Tau, NfL and APOE ϵ status and NeuroCart tests, age, grip strength and level of education that distinguishes between positive and negative A β CSF in healthy elderly.

Exploratory objective:

To determine the correlation between AD-specific biomarkers in CSF (Aβ 1-40 and 1-42, Tau proteins, NfL) and the NeuroCart scores in a cohort of 200 healthy elderly subjects.

To determine the correlation between AD-specific biomarkers in plasma (Aβ 1-40 and 1-42, Tau proteins, NfL) the NeuroCart scores in a cohort of 200 healthy elderly subjects.

To determine the correlation between AD-specific biomarkers in CSF (Aβ 1-40 and 1-42, Tau proteins, NfL) and in plasma in a cohort of 200 healthy elderly subjects.

To determine the correlation between APOE ϵ genotype and the A β /Tau/NfL concentrations in CSF in a cohort of 200 healthy elderly subjects.

To determine the correlation between APOE ϵ genotype and the A β /Tau/NfL concentrations in plasma in a cohort of 200 healthy elderly subjects.

To characterize the cohort of healthy elderly subjects in order to yield norm scores for specific NeuroCart tests in all subjects.

To characterize the plasma biomarkers across multiple times of day to gain understanding of intraand inter-subject variability, and thus diurnal fluctuation.

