4.4 Study population subgroups

General cognitive functioning, dementia status and depressive status will be assessed at pre-study screening. All subjects eligible according to the in- and exclusion criteria will be entered in the study. Subjects will be asked to give consent for a LP.

Plasma levels of A β 40, A β 42 and NfL, APOE ϵ status and NeuroCart tests of the 200 subjects will be used to define an algorithm that will be able to improve the efficiency of finding healthy subjects who have an A β positive (CSF) profile. The subjects will be divided in a group yielding subjects who are suspected of AD pathology (ADpath+) by the algorithm and subjects who are suspected to be without AD pathology (ADpath-)

To confirm the correct classification potential of the algorithm, the outcome will be compared to the CSF Aβ outcome of the subjects. CSF ADpath+ and a CSF ADpath- defined by an Aβ 1-42 CSF

level ≤450 pg/mL for ADpath+ subjects and an Aβ 1-42 CSF level ≥451 pg/mL for ADpath- subjects, will be used to differentiate between the two groups.

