9.8 CNS and biochemical endpoints

9.8.1 NeuroCart

All parameters will be listed by subject.

Parameters will initially be analysed without transformation, but if the data suggest otherwise, log-transformation may be applied.

Descriptive statistics will be used to summarize the data. Data will be graphically processed for visual inspection.

In order to develop an algorithm that can classify the subjects between ADpath+ and ADpath- there will be a two-step procedure. In the first step 500 bootstrap samples will be generated out of the original data and logistic regression with LASSO penalization (in order to account for the expected small event per variable ratio) in each of the bootstrap samples with all the candidate variables (CNS and biochemical outcome variables, age and educational level) will be performed. Out of all the candidate variables the ones that consistently and most frequently appear in the bootstrap models will be selected. Hence, in this first step the variable selection will take place. In the second step another 500 bootstrap samples will be generated and logistic regression will be performed (with penalization if necessary) in each of the bootstrap samples. This time only the variables that were selected in step 1 will be entered in the model. The estimates out of all the bootstrap models will be averaged and used in order to obtain predictions in the original data. Step two will result in the bootstrap-corrected predictions that will be assessed in terms of calibration (calibration slope), discrimination (c-index) and squared mean prediction error.

To investigate the relationship between biomarkers and gene carriers and NeuroCart scores, correlations and regression analyses will be used.

NeuroCart scores will be analysed with an analysis of variance (ANOVA) and/or multivariate analysis of variance (MANCOVA) to estimate differences between the groups of elderly with different Aβ status.

The intra- and inter-individual diurnal fluctuation will be investigated with mixed-model analysis.

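### The protocol reports the CSF Aβ42/Aβ40 ratio as better than Aβ42 alone but gives the ratio no part in building or checking the algorithm

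*Protocol*

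**What the plan says.** Section 7.1.4 (CSF sampling) cites a study which found that "calculating the ratio between Aβ40/Aβ42 is significantly better in detecting amyloid deposition in prodromal AD", and in separating AD patients from healthy elderly, "than (only) measuring lowered Aβ42 and will therefore also be calculated in the current study".

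Elsewhere the protocol treats the ratio as follows:

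- **CSF endpoints (6.3).** The ratio is listed: "Aβ concentration (1-40, 1-42 and 1-42/1-40 ratio".
- **Plasma endpoints (6.3).** The list stops at the two peptides: "Aβ concentration (1-40, 1-42".
- **Main objective (section 2).** The algorithm is to be "based on the plasma biomarkers: A β 40, A β 42, t-Tau, p-Tau, NfL", together with APOE status, NeuroCart tests, age, grip strength and education. No ratio is named.
- **Reference status (synopsis, section 1 and 4.4).** It is set by CSF Aβ 1-42 alone: "Aβ 1-42 CSF level ≤450 pg/mL for ADpath+ subjects".
- **Selection (9.8.1).** LASSO logistic regression is run in 500 bootstrap samples, and the most frequently selected variables go forward. The same section says "Parameters will initially be analysed without transformation" and then allows log-transformation if the data suggest it.

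No section gives a ratio cut-off or a second definition of Aβ status.

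**The concern.** The protocol gives a reason to look at the ratio and then leaves it out of both ends of its main analysis. Two consequences follow.

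**Predictors.** Where the two plasma peptides vary together between people, the information about amyloid may sit in their difference on the log scale. Entered separately, they can carry that information only as a pair with opposite coefficients. An L1 penalty charges for both coefficients, so selection can lose one or both, and step 2 works only with what step 1 kept.

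**Reference.** The c-index, calibration slope and prediction error in 9.8.1 are all judged against the Aβ 1-42 label. With no second label planned, the reader cannot see whether the conclusion depends on that choice.

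**Working it through.** **1. The plan's own figure.** Sections 1.1.4 and 4.1 plan 200 subjects, at least 100 of them over 70, with expected positivity of 23% (over 70) and 19% (applied to 65-70). 100 × 0.23 + 100 × 0.19 = 42 positives, as stated. 42/200 = 21%, the prevalence used below.

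**2. Assumed inputs.** The documents give no distributions, so these are illustrative. The plasma signal is assumed to lie wholly in log(Aβ42/Aβ40), with within-group SD 0.15. Log Aβ40 has SD 0.15 to 0.40 and no shift of its own.

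**3. Why the penalty matters.** log(Aβ42/Aβ40) = log Aβ42 − log Aβ40. Take SD 0.25 for log Aβ40:

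- SD of log Aβ42 = √(0.25² + 0.15²) = 0.292.
- Correlation of the two logs = 0.25/0.292 = 0.86. With SD 0.15 for log Aβ40 it is 0.15/0.212 = 0.71.
- With standardised candidates, a coefficient β on the log ratio costs |β| × 0.15 in L1 penalty. The same predictor built from the pair costs |β| × (0.25 + 0.292) = |β| × 0.542, which is 3.6 times as much. With SD 0.15 it is (0.15 + 0.212)/0.15 = 2.4 times.

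**4. Without a penalty.** In large-sample logistic models (N = 200,000), the ratio gives a c-index of 0.64 at a shift of 0.5 SD and 0.76 at 1.0 SD. The untransformed pair gives 0.64 and 0.75 to 0.76, and the log pair 0.64 and 0.76. Practically nothing is lost while both peptides stay in. If only Aβ42 stays, the value at 1.0 SD falls to 0.60 to 0.69.

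**5. With LASSO at n = 200.** First set: 50 noise candidates, 60 datasets, penalty chosen for best test c-index, and the ratio replacing the untransformed pair.

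| SD log Aβ40 | Shift (ratio SDs) | Ratio | Pair | Loss | Both peptides kept |
|---|---|---|---|---|---|
| 0.15 | 1.0 | 0.759 | 0.684 | 0.075 | 52% |
| 0.15 | 1.3 | 0.819 | 0.774 | 0.045 | 80% |
| 0.25 | 1.0 | 0.758 | 0.641 | 0.117 | 55% |
| 0.25 | 1.3 | 0.822 | 0.735 | 0.087 | 83% |

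Second set: 59 noise candidates, penalty by 5-fold cross-validation, SDs 0.25 (shared) and 0.14 (ratio), log shift 0.12 (0.12/0.14 = 0.86 SD). The pair gives 0.55. With the ratio available the c-index is 0.69 to 0.71 over two runs, so the loss is 0.14 to 0.16. Both peptides were kept in 10% to 18% of fits over three runs, and the ratio in 98% to 100%. At a log shift of 0.20, both peptides were kept in 80% of fits and the pair reached 0.75.

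Together the loss is about 0.05 to 0.16, and its size is set largely by the assumed shift.

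**6. Two CSF labels compared.** Write log CSF Aβ42 as shared production plus log ratio. Assume production SD 0.15 to 0.30, ratio SD 0.12 to 0.15, a shift of 0.5 to 0.6 in positives, and each label cut at its lowest 21%. In 1,000,000 simulated subjects the two labels differ in about 4.5% to 16%, or about 9 to 33 of 200. This measures discordance between two labels. It does not say which label is right.

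**The case against.** - **The evidence is narrower than the use made of it.** Section 7.1.4 reports one study, in CSF, in prodromal AD and in AD versus healthy elderly. A reader might infer that the protocol itself calls the plasma ratio better, or better in healthy elderly. It does not; that extension is ours. This stands, and it is why the plasma part is conditional.
- **The label is a deliberate choice.** The background sets lowered CSF Aβ as the target, and 7.1.4 promises only that the ratio will also be calculated, which 6.3 honours. A reader might infer that subjects are mislabelled and that every c-index is therefore pulled towards 0.5. That would need the ratio to be the truth and the errors to be unrelated to the predictors. The documents support neither.
- **The pair already contains the ratio.** On the log scale the two peptides span it, 9.8.1 allows log-transformation, and an unpenalised model loses almost nothing. So one cannot say that the peptides must enter untransformed. But log-transformation does not remove the penalty cost in step 3 of the working, and step 1 of the plan is penalised.
- **The simulations build in their answer.** They place all the signal in the ratio and use single LASSO fits in place of the planned two-step bootstrap. This is fair as to size. A reduced version of the two-step procedure did not remove the loss, so the direction holds under the assumption.
- **The statistical analysis plan could add all this.** It could. But the protocol itself names the predictors and fixes the only reference, so the change belongs there too.

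**Conclusion.** The point holds as an inexpensive improvement to the plan. The protocol cites evidence in favour of the ratio, will assay both peptides in both fluids (7.2.3), and gives the ratio no role in its main objective.

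If the plasma signal lies in the Aβ42/Aβ40 contrast, penalised selection from separate peptides may cost about 0.05 to 0.16 in c-index at n = 200. If the signal does not lie there, or the model is unpenalised with both peptides kept, the cost is close to nil. The true size cannot be derived from the documents.

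On the reference side, the conclusion is only that dependence on the label should be shown. The discordance of about 9 to 33 in 200 rests on assumed distributions and is not an error rate for Aβ 1-42.

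**What to change.** - Add plasma Aβ42/Aβ40, as a log ratio, to the plasma list in 6.3, to the main objective and to the candidate variables in 9.8.1.
- Keep CSF Aβ 1-42 at 450 pg/mL as the stated reference. The referral rule in 4.5 is not touched.
- Pre-specify one sensitivity analysis that repeats the whole two-step procedure with status defined by CSF Aβ42/Aβ40. Fix its cut-off before the CSF results are linked to plasma and NeuroCart data, so that it cannot be tuned to the algorithm.
- Report how many subjects the two labels classify differently.

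**Cost.** One derived variable, one extra run and some wording; no new assay or visit. The downsides are one more candidate in an already large pool, and a second label whose cut-off may have to be derived in-sample with about 42 expected positives. That cut-off would be imprecise, so this analysis should stay secondary.
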